about objects that would be targets for navigation or action. In this group, participants will be stationary and only be asked to rotate/pan their head to acquire camera-generated targets. In Group 2, egocentric localization and spatial image updating tasks test how well the system provides spatial parameters, particularly distance, from optical flow and non-visual sources, leading to the formation of the spatial image. Finally, Group 3 tasks test the system in its function of guiding navigation and assess learning effects.

In all three groups, various instantiations of the system are contrasted as follows. The **Basic system** is the standard Argus II device. The **Augmented system** enhances the imagery for visual feedback compared to the standard Argus II system by decluttering the scene and adding discriminative features to convey object identities. The features to be utilized will be determined after tests in Group 1, but the general goal is to add spatial and/or temporal uniqueness without cluttering the display. The third system, the **Augmented + Modal system**, adds non-visual cues. Initially, we are targeting two non-visual augmentation modalities including (i) verbal and non-verbal auditory feedback along with spatial sound for purposes such as to convey the identity, distance, and direction of objects relative the user and (ii) haptic feedback for purposes such as to direct users how to adjust their head azimuth and elevation in order to acquire a landmark or waypoint within their field of view.

The enhanced imagery information for visual feedback used in the Augmented and Augmented + Modal modes of the system will be computed by the navigation system developed in this study and communicated to the Argus II using a built-in video input on the Argus II that enables visual information provided from an external source to be displayed by the user's implant. No alterations, including software or hardware changes, will be made to a participant's Argus II system during this study.

B Background

B1 Prior Literature and Studies

The Argus II system is a fully portable medical device approved by the FDA for commercial sale in the United States under the Humanitarian Device Exemption (HDE) program. It consists of implanted and external components (see Figure 1).

[figure not shown]

Figure 1 - Argus II Retinal Prosthesis System

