These hypotheses will be tested statistically with sighted subjects (see Section F) by measuring proportion correct assessments as well as through bias and precision measurements. Argus II subjects will be assessed individually to determine whether augmentation leads to lower error, and their error will be quantified through comparisons with the sighted subjects.

F Statistical Plan

F1 Sample Size Determination and Power

No significance testing will be possible with Argus II participants due to the small number of people expected to be recruited for each Argus II participant group in this study (approximately 5).

Importantly, however, we will use the sighted subjects, who simulate the performance of Argus II users through the head mounted display conveying information similar to what is perceived by Argus II users, as a baseline. As described in G3, we characterize performance by Argus II users on any given task relative to this baseline.

In particular, for tests with sighted subjects, we use within-subject factorial designs and test with conventional ANOVA statistics; inter-subject correlations between abilities tests can also be computed. We use sample sizes based on prospective power analysis. A sample size of 20-30 subjects was calculated with [9] to achieve

a power greater than 0.80 at the 0.05 level of significance, using effect sizes from previous studies reporting perceived spatial layout in within-subject designs [10]. As a more general point, the experiments use a within-subject design, in which every subject provides a replicate of the entire study. In psychophysical research (i.e., where a physical variable is parametrically explored), these designs are typically done with populations on the order of 10-20 participants. The proposed sample is also consistent with similar studies of navigation by spatial updating (e.g., [11]).

F2 Analysis Plan

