For each measure, the Argus II participants will be characterized by the z-score distance of their performance from the sighted participants (as computed with their mean and variance). We will use two other approaches to assess the Argus II participants' performance: (i) Use standards from the literature for basic psychophysical effects, including setting .2 as an effective d' score for 2- choice discrimination, based on Cohen's d effect-size statistics; setting 25% as the expectation for a size difference threshold, and setting a standard of 15° for absolute pointing error based on screening cutoffs in previous work. (ii) Set standards by considering the device capabilities; in particular, use distance expressed in device pixels between target and pointing locations in order to measure localization error. Finally, we intend to test the effects of learning by assessing performance over time. For this, we will fit trends to the measures over repeated trials and assess the linear component for a positive slope.

F3 Statistical Methods

See previous sections for additional information about the methods employed for this study.

G Data Handling and Record Keeping

G1 Confidentiality and Security

Every effort will be made to keep Personally Identifiable Information (PII) associated with the study confidential: (1) subjects will be assigned a code number and only the code number will be used to identify the limited clinical information that will be analyzed; (2) the computers on which the data will be stored are password protected and all of them are located in offices with key locks; (3) written documents concerning the study will be kept in locked cabinets; (4) all personnel involved in human subject testing will have completed the appropriate HIPAA training and be fully aware of the need for confidentiality regarding PII. No health information will be acquired for this study.

G2 Training

All study team members are required to take IRB compliance training. At a minimum, this consists in Basic Human Subjects Research (CITI) training, Health Privacy Issues for Researchers training, and Conflict of Interest and Commitment training per JHM IRB policy, in addition to Good Clinical Practice training as required by NIH. PIs are also required to take Research Ethics Workshops About Responsibilities and Duties of Scientists training.

G3 Records Retention

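### Each Argus II user is to be judged on whether augmentation lowers error, but F2 estimates no within-user change from Basic with its uncertainty, and no system order is stated

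*Combined protocol and SAP*

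**What the plan says.** C1 places the primary aim in Argus II recipients. A2 defines three systems (Basic, Augmented, Augmented + Modal) and says of the three task groups: "In all three groups, various instantiations of the system are contrasted as follows". D1 repeats the comparison with Basic for both phases. E6 assigns the statistical tests of the hypotheses to the sighted subjects, and for the implanted users says "Argus II subjects will be assessed individually to determine whether augmentation leads to lower error", with their error also set against that of the sighted subjects.

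F1 then states "No significance testing will be possible with Argus II participants due to the small number of people expected to be recruited"; the sentence goes on to give about 5 for each Argus II participant group. F1 adds "As described in G3, we characterize performance by Argus II users on any given task relative to this baseline", and describes the design in these words: "the experiments use a within-subject design, in which every subject provides a replicate of the entire study".

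F2 gives the methods for Argus II users. First, "For each measure, the Argus II participants will be characterized by the z-score distance of their performance from the sighted participants", computed from the sighted mean and variance. Second, fixed standards: d' of 0.2, a 25% size threshold and 15° pointing error. Third, localization error in device pixels. Finally, for learning, "we will fit trends to the measures over repeated trials and assess the linear component for a positive slope". F3 only refers back to earlier sections.

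**The concern.** E6 poses a question within each person: is this user's error lower with an augmented system than with Basic? An answer needs the difference between systems for that user and a measure of its uncertainty. F2 supplies neither. A z-score places the user relative to sighted people. A fixed standard classifies a level of performance. Pixel error, if reported by system, would show a change but not whether it exceeds trial-to-trial noise. The learning slope describes change over time, and F2 does not say that it will be used to adjust the system comparison.

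Order is the second gap. A2 says "Group 3 tasks test the system in its function of guiding navigation and assess learning effects", D1 describes training, and section 2.c expects fatigue. The protocol nevertheless states no sequence, randomisation or counterbalancing of systems, and no number of trials per system.

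At stake is what the study can say about the people named in its primary aim. They are few, and order cannot be repaired once they have been tested.

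**Working it through.** **1. The plan's own sample size.** F1's 20-30 applies to sighted subjects (power above 0.80 at the 0.05 level). F1 gives no numerical effect size, SD, correlation or sidedness, so the figure cannot be reproduced. Back-solving a two-sided paired t-test for 80% power gives a standardised difference of 0.66 at n = 20 and 0.53 at n = 30. The range is plausible but unverifiable, and it does not bear on the per-user question, for which the documents give no figure.

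**2. What the head count limits.** Across n users, the smallest two-sided sign-test p is 2 × 0.5^n. For n = 5 this is 2 × 0.03125 = 0.0625; for n = 6 it is 0.031. So under this test F1's reason has force at 5 users. B2 and D1 allow 5 to 15 in total.

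**3. What limits a within-user comparison.** Assume independent trials and 55% correct on Basic against 80% on Augmented (neither rate is in the documents). The Newcombe 95% interval for the difference d = p2 − p1 uses the Wilson limits (l, u) of each proportion:

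- lower limit = d − √[(p2 − l2)² + (u1 − p1)²]
- upper limit = d + √[(u2 − p2)² + (p1 − l1)²]

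At 40 trials per system, 22/40 has Wilson limits 0.398 to 0.693 and 32/40 has 0.652 to 0.895. Then:

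- lower = 0.25 − √(0.148² + 0.143²) = 0.045 (0.0445 before rounding)
- upper = 0.25 + √(0.095² + 0.152²) = 0.429

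| Trials per system | Correct, Basic vs Augmented | 95% interval for the gain | Chance the interval excludes zero |
|---|---|---|---|
| 20 | 11 vs 16 | −0.039 to 0.490 | 0.41 |
| 40 | 22 vs 32 | 0.045 to 0.429 | 0.67 |
| 60 | 33 vs 48 | 0.082 to 0.399 | 0.85 |

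The number of users appears nowhere in this calculation.

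**4. Order.** Assume that Basic always comes first, that there is no true effect, and that performance steps up by g log-odds between the two halves. At a baseline log-odds of 0.4, proportion correct is 1/(1 + e^−0.4) = 0.599.

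- g = 0.3: 0.668 − 0.599 = 0.070 (rounded from 0.0695)
- g = 0.5: 0.711 − 0.599 = 0.112

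With baselines varying between users (normal, mean 0.4, SD 0.4) and 40 trials per system, simulation gives mean spurious gains of about 0.067 and 0.109. A single user's interval lies wholly above zero in about 9 to 10% and 18% of cases, where 2.5% is expected.

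**5. z-score reference.** F2 does not name the system whose sighted mean and variance are used. If sighted Basic and Augmented means differ by 1 sighted SD (assumed, equal SDs), the same performance by one user moves by 1.0 in z according to the reference.

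**6. Pointer.** F1 refers to G3 for the comparison with the sighted baseline. G3 is Records Retention; F2 appears to be meant.

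**The case against.** The strongest reply is that this is a pilot, described as an observational case series, in which individual description is legitimate. F1's full sentence refers to each participant group, so it already reads as a group-level statement. F2 plans repeated trials, so trial-level data will exist and an interval could be computed later. Most of this stands. What remains is that the plan makes a per-user determination in E6 and specifies no method for it in F2.

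Some stronger readings are tempting and are not supported:

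- **E6 and F1 contradict each other.** They do not. One concerns individuals, the other inference from a group of about 5.
- **Benefit could never be separated from noise or practice.** With trial-level data, noise can be estimated. Practice is a problem only if the order used is confounded with system.
- **Basic is run first.** D1's narrative, which names Basic and then turns to the augmented systems, might suggest it, but no sequence is stated. The figures in step 4 are conditional on that assumption.
- **A particular test, block count, multiplicity rule or z-score reference is required.** Nothing in the documents establishes this. A fixed reference and a same-system reference answer different questions, and a fixed ABBA sequence is not shown to be inadequate. D1 already specifies unfamiliar environments, so a separate rule on layouts is not needed here.

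**Conclusion.** The point holds, as a cheap improvement. Followed as written, F2 does not answer the per-user question set in E6, and F1's head-count reason does not excuse the omission. Under the assumed success rates, 40 trials per system would give a per-user interval of roughly 4 to 43 points around a 25-point gain. How precise the real comparison would be cannot be judged, because no trial counts are given.

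The order risk is conditional. It is about 7 to 11 spurious points only if one fixed sequence such as Basic first is used and learning is a step of 0.3 to 0.5 log-odds. All trial counts, success rates and learning sizes are illustrative assumptions. Any per-user result applies to that user, so caution about generalising from about 5 people remains.

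**What to change.** 1. **F2, contrast.** For each Argus II user and each main measure, report Augmented minus Basic and Augmented + Modal minus Basic, each with a 95% interval from that user's repeated trials. Adjust for trial order, or build the interval from block means where trials are run in blocks. State the trials per system, and say that the result applies to that user only.
2. **Order.** Randomise or counterbalance system order within each user, with a scheme that balances all three systems over time.
3. **F1.** State that the exclusion of testing concerns inference across users, and correct the G3 pointer.
4. **z-scores.** Name the system whose sighted mean and variance define each z-score. Do not read a change in z across systems as a gain if the reference changes too.

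**Cost.** Some added text, a little more analysis and more switching between systems within sessions; D1 already notes setup time for Argus II users. No extra participants are needed. Block means lose some precision when trials are in fact independent. With five blocks per system and 55% against 80% correct (both assumed), power is about 0.35, 0.58 and 0.75 at 20, 40 and 60 trials per system, against 0.41, 0.67 and 0.85 for the trial-level Newcombe interval.

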We will recruit approximately 25 to 35 normally sighted adults, and approximately 5 to 15 retinal prosthesis users. We will test sighted participants in order to establish baseline levels for processing the information delivered when the optic nerve is healthy and intact. We do not claim that Argus II users will be comparable in performance; in fact, testing will be directed at the implanted users to characterize a range of performance compared to baseline.

Our Johns Hopkins University Applied Physics Laboratory (JHU/APL), Johns Hopkins Medicine Wilmer Eye Institute (JHM/Wilmer), and Second Sight teams have been collaborating for the past several years to advance the capabilities of the Argus II system and improve performance of Argus II recipients, including developing capabilities for object recognition and stereo vision, and have extensive experience in designing and developing SLAM software and algorithms in the field of robotics. In addition to the investigators at Wilmer Eye Institute and Second Sight who have extensive experience in working with retinal prosthesis users, our team includes [name], who has a long history of research working with visually impaired individuals and studying the impact of human neurophysiology and psychology on the design of instruments and devices that can be used as navigational aids for the blind.

C Study Objectives

C1 Primary Aim

The primary aim of this study is to ascertain whether our system allows Argus II recipients to form a “spatial image” of their environment, that is, a continuously updated representation of locations in three dimensional space that supports volitional action for independent navigation.

C2 Rationale for the Selection of Outcome Measures

The outcome measures derive directly from the goals of this study, namely the ability to identify and localize targets, with and without movements, and navigate through a field comprised of these targets.

D Study Design

D1 Overview or Design Summary

Testing will be conducted at JHU/APL, JHM/Wilmer and at JHU Homewood campus.

This study will be conducted with three different sets of participants.

- One set of eligible participants will consist of Argus II users, with a total of approximately 5 to 15 such participants expected to be recruited for this study. These tests may take place across all test sites.

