The identification and localization tests (Group 1) use common psychophysical judgments such as the following: discriminating between two alternatives by saying which is present in the field of view, touching a tablet computer to indicate the apparent location of a target in the frontal plane, and looking for targets by rotating the head and pointing when one is found. In the egocentric localization and spatial updating tasks (Group 2), the participants will make similar psychophysical judgments, but now in the context of movement, for example requiring the participants to walk several meters towards a visible target. For example, in some trials participants may be asked to move backwards to the origin (with aid of a guide), then verbally estimate the distance to the target or point with a joystick toward it. Similarly, in other trials, after walking toward the target with vision present, they may be asked to move forward a short distance without vision and make the same types of judgments.

The second phase of testing (Group 3 tasks), will involve using the information gleaned from the first phase to assess participants' ability to navigate through an unfamiliar environment. This phase will again compare user performance using the

Basic system with user performance using the **Augmented** and **Augmented + Modal** systems where contextual information associated with the task is conveyed to users via enhanced visual, auditory, and haptic modalities.

Our algorithms for mapping the environment and localizing the user will provide the core autonomous navigational capability of the system. As the user traverses their environment, object recognition will be used in concert with the spatial localization and mapping technology to automatically detect key navigational features (e.g., doors, signs, etc.) and store these locations in the map. Once stored in the map, these semantic attributes may then be verbally queried by the user for navigation, e.g., “lead me to the nearest restroom”.

The enhanced imagery generated by the **Augmented** and **Augmented + Modal** systems will be achieved without modifying the Argus II device. The imagery content for these modes will be computed by algorithms of the navigation system and then transmitted via video link to the Argus II for display to the Argus II user.

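### F2 and E6 give no way to read Argus II users' distance judgements: an uncut error z-score and an unruled 'lower error' comparison do not show whether answers follow true distance

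*Combined protocol and SAP*

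**What the plan says.** C1 puts the question about implant users: "The primary aim of this study is to ascertain whether our system allows Argus II recipients to form a “spatial image” of their environment". A2 ties Group 2 to that aim, because its tasks "test how well the system provides spatial parameters, particularly distance, from optical flow and non-visual sources, leading to the formation of the spatial image". D1 repeats the emphasis on distance. It describes trials "requiring the participants to walk several meters towards a visible target", after which participants may return to the origin and "then verbally estimate the distance to the target or point with a joystick toward it".

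F2 then sets out how Argus II users are assessed. The general rule is "For each measure, the Argus II participants will be characterized by the z-score distance of their performance from the sighted participants", with no cutoff. Numeric standards follow for 2-choice discrimination (d' of 0.2), size (25%) and absolute pointing error (15°). Localization error gets a unit, device pixels, but no value. Judged distance gets neither. F2's one use of a slope is for learning over repeated trials, not for response against true distance.

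E6 adds that each Argus II user is assessed for lower error under augmentation, and names proportion correct, bias and precision without defining them. F1 rules out significance testing in Argus II users because few are expected (about 5 per group). F1 also refers to G3 for the baseline comparison, but G3 covers records retention and the method is in F2. B2 adds: "We do not claim that Argus II users will be comparable in performance".

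**The concern.** A z-score against sighted users says how large a user's error is compared with theirs. It does not say whether the user's answers move with the target. A user with no distance information who always names a mid-range value makes moderate errors, and can sit close to sighted subjects whose own estimates are biased or variable. Since B2 disclaims comparability, no z value has a natural meaning as success or failure.

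The other standards do not fill the gap. If a participant walks straight toward a target and backs up along the same line, the target's direction does not change, so pointing within 15° needs no distance information. Pixel error is measured in the image plane, not in depth.

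At stake is the distance component of the C1 conclusion. Someone would have to decide after seeing the data which z values, or how much reduction in error, count in favour of a spatial image.

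**Working it through.** **The plan's own figure.** The only power statement is 20-30 sighted subjects for power above 0.80 at the 0.05 level. It gives no effect size and so cannot be reproduced. For a two-sided paired t-test at 80% power, N = 20 detects a standardised difference of 0.66 and N = 30 detects 0.53. It does not cover Argus II users or this question.

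**Assumed inputs (not in the documents, which say only that participants walk several meters).** Targets at 2, 3, 4, 5 and 6 m, four trials each (20 trials). 25 sighted subjects, within the plan's 20-30. Mean sighted scale factor 0.7-1.0, between-subject log-SD 0.15-0.35, trial noise 0.5-1.0 m. The metric is mean absolute error, signed so that a negative z is worse than the sighted mean.

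**Why a constant answer can look ordinary.** Ignoring trial noise:
- A user who always says 4 m has mean absolute error (2 + 1 + 0 + 1 + 2)/5 = 1.2 m.
- A sighted subject with scale factor 0.7 has error 0.3 × 4 = 1.2 m, the same.
- Sighted subjects who are unbiased on average with log-SD 0.35 have mean error of roughly 0.80 × 0.35 × 4 = 1.1 m.
- With log-SD 0.15 the figure is 0.80 × 0.15 × 4 = 0.5 m, and the guesser starts to stand out.

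**Simulation, 18 settings across these ranges, z = −(user error − sighted mean)/sighted SD.**
- Guess at 4 m: z ≥ −2 in about one third to all runs, and in a majority of runs in 16 of 18 settings. The lowest shares (about 0.35 and 0.48) come with scale 1.0 and log-SD 0.15. With scale 0.85 and log-SD 0.15 the share is 0.72-0.76.
- Guess 1 m off centre: the minimum falls to about 0.12.
- The unset cutoff matters. In the least favourable central-guess setting the guesser passes in about 19% of runs at −1.645, 35% at −2 and 77% at −3.

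**A second model, using E6's metrics.** Sighted mean slope 0.6-0.8, trial CV 20-40%, between-person gain SD 0.2-0.3, five trials per target, targets spanning 2-4, 2-6 or 1-8 m. A central constant guesser is about 1.2-1.3 SD better than the sighted mean on absolute bias and 2.7-4.2 SD better on repeat precision. On mean absolute error the result runs from 1.4 SD better to 2.2 SD worse, the latter with a wide range and low noise. On the slope of response against target, the same guesser is about 1.2-3.1 SD below the sighted mean in every scenario.

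**The E6 comparison.** A guesser who behaves identically under both systems has no systematic gain. With trial noise, error is nevertheless lower under augmentation in about half of runs (48-53%). Without a rule, that direction alone is uninformative.

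**The slope alternative.** The sum of squares of true distance is 4 × (4 + 1 + 0 + 1 + 4) = 40 for 20 trials. With 1.0 m noise the standard error of the slope is 1/√40 = 0.158.
- True slope 0: the lower 95% limit exceeds 0 in about 2.5% of runs per system. Across two augmented systems, if independent, this is 1 − 0.975² = 4.9%.
- True slope 0.5, 20 trials: 0.5/0.158 = 3.16, power about 85% (over 99% with 0.5 m noise).
- True slope 0.5, 10 trials: standard error 1/√20 = 0.224, power about 50%.
- Difference of 0.5 from a zero Basic slope, 20 trials per system: standard error 0.158 × √2 = 0.224, power about 58%.

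**The case against.** The strongest reply is that the z-score is offered as a description, not a pass mark. A2 calls the study an observational case series, D2 a pilot, and F1 disclaims significance testing in Argus II users. No text says that a z near 0 counts as success. That is correct, but F2 does set reference values for three other measures, so giving none for the parameter A2 stresses is an inconsistency and not just a descriptive style. F1's reason for avoiding tests is the small number of people. A per-user slope draws on that user's trials and speaks only about that user.

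A reader might infer two stronger things that the documents do not support. The first is that the z-score is the only yardstick. E6 also plans a within-person comparison of error with and without augmentation, in which a constant guesser shows no systematic gain. What it lacks is a rule. The second is that the study cannot answer C1 at all. C1 also draws on pointing, which has a standard, on Group 3 navigation, and on the statistical tests of the spatial-image hypothesis in sighted subjects. Those tests do not by themselves answer a question about recipients, but they are relevant evidence.

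It is also fair to object that the guessing figures rest on inputs the plan does not give and on a guess near the centre of the range. They show what can happen, not what will.

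**Conclusion.** The point holds for judged distance. The plan gives Argus II users an error z-score with no cutoff and a lower-error comparison with no decision rule, and neither tests whether answers follow true distance. The distance part of the C1 conclusion would be a post hoc reading. Under the assumed inputs, a user with no distance information and a central guess reaches z ≥ −2 in about one third to all runs. The share falls when the guess is off centre or when sighted judges are unbiased and uniform. The size depends on target range, trial count, sighted bias and spread, noise and choice of error metric, none of which the plan fixes. The absence of a distance standard and of any decision rule depends on none of these. This should be corrected, but it does not invalidate the study.

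**What to change.** In F2, for each Argus II user and each system (Basic, Augmented, Augmented + Modal), regress judged on true target distance over the Group 2 trials, with at least three true distances. This fits F1's description of designs that vary a physical variable parametrically. Report each slope with its 95% confidence interval. Read a lower limit above 0 under an augmented system as evidence that distance information is present. Report the slope difference from Basic with its 95% interval before crediting any gain to the new system. Report the number of users meeting this out of those tested, with an exact 95% interval. Keep error size and the E6 comparison, define bias and precision, and state that the z-score is descriptive and not a pass mark.

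The cost is a few sentences and three simple regressions per user, with no extra participants. The plan does not state the number of distances or trials, so Group 2 may need more of either. A positive slope shows information, not accuracy. Power depends on trials per user, and the difference from Basic is harder to show than the slope itself. With about 5 users the exact interval is wide: 3 of 5 gives 15% to 95%.
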